1.2.1 Adverse events (AEs)

Summary tables for AEs have to include only AEs that started or worsened during the on-treatment period, the **treatment-emergent** AEs. However, all safety data (including those from the post-treatment periods) will be listed and those collected during the post-treatment period are to be flagged.

The incidence of all treatment-emergent AEs (number and percentage) will be summarized by system organ class (SOC), preferred term, and maximum severity, relation to study treatment.

Deaths reportable as SAEs and non-fatal serious AEs will be listed by patient.

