**Table 3-1 Objectives and related endpoints**

Objective	Endpoint	Analysis
Primary To collect and assess long term safety of everolimus	Frequency and nature of AEs	Refer to Section 10.4

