### **6.1.5     Treatment duration**

Patients will continue to be treated in the roll-over protocol until they are no longer benefiting from their everolimus treatment as defined in the parent protocol (disease progression), they develop unacceptable toxicities, they withdraw consent, they are non-compliant to the protocol, the investigator feels it is no longer in the patient's best interest to continue everolimus therapy or the patient dies, whichever comes first. A patient will reach the end of the roll-over study when everolimus treatment is permanently discontinued.

The study is expected to remain open for 5 years or until such time that enrolled patients no longer need treatment with everolimus, whichever comes first.

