#### **7.1.4.1 Withdrawal of consent**

Patients may voluntarily withdraw consent to participate in the study for any reason at any time. Withdrawal of consent occurs only when a patient does not want to participate in the study any longer, and does not want any further visits or assessments, and does not want any further study related contact.

Novartis will continue to retain and use all research results that have already been collected for the study evaluation. All biological samples that have already been collected may be retained and analyzed at a later date (or as required by local regulations).

If a patient withdraws consent, the investigator should make a reasonable effort (e.g. telephone, e-mail, letter) to understand the primary reason for this decision and record this information.

Everolimus must be discontinued and no further assessments conducted.

Further attempts to contact the patient are not allowed unless safety findings require communication or follow up.

Patients may be withdrawn from the study if any of the following occur:

- Death
- Lost to follow-up
- Staying in the study would be harmful
- Patient/guardian decision
- Physician decision
- Non-compliance to protocol requirements
- Protocol deviation
- Pregnancy
- Study terminated by sponsor
- Unsatisfactory therapeutic effect

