# 8 Safety monitoring and reporting

## 8.1 Adverse events

### 8.1.1 Definitions and reporting

An AE is defined as the appearance of (or worsening of any pre-existing) undesirable sign(s), symptom(s), or medical condition(s) that occur after patient's signed informed consent has been obtained.

Abnormal laboratory values or test results occurring after informed consent constitute AEs only if they induce clinical signs or symptoms, are considered clinically significant, require therapy (e.g., hematologic abnormality that requires transfusion or hematological stem cell support), or require changes in study medication(s).

AEs that begin or worsen after informed consent should be recorded in the AEs eCRF. AE monitoring should be continued for at least 30 days after the last dose of everolimus. AEs (including lab abnormalities that constitute AEs) should be described using a diagnosis whenever possible, rather than individual underlying signs and symptoms. When a clear diagnosis cannot be identified, each sign or symptom should be reported as a separate AE.

AEs will be assessed according to the Common Terminology Criteria for Adverse Event (CTCAE) version 4.03.

If CTCAE grading does not exist for an AE, the severity of mild, moderate, severe, and life-threatening, corresponding to Grades 1 - 4, will be used. CTCAE Grade 5 (death) will not be used in this study; rather, information about deaths will be collected in the End of Treatment eCRF page.

The occurrence of AEs should be sought by non-directive questioning of the patient during the screening process after signing informed consent and at each visit during the study. AEs also may be detected when they are volunteered by the patient during the screening process or between visits, or through physical examination, laboratory test, or other assessments. As far as possible, each AE should be evaluated to determine:

1. The severity grade (CTCAE Grade 1-4)
2. Its duration (Start and end dates or Ongoing at End of Study)
3. Its relationship to the study treatment (Reasonable possibility that AE is related: No, Yes)
4. Action taken with respect to study or investigational treatment (none, dose adjusted/ temporarily interrupted, permanently discontinued, concomitant medication taken, non-drug therapy given, hospitalization)
5. Whether it is serious, where a SAE is defined as in [Section 8.2.1](#)

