### **10.4.2 Adverse events (AEs)**

Summary tables for AEs have to include only AEs that started or worsened during the on-treatment period, the **treatment-emergent** AEs. However, all safety data (including those from the post-treatment periods) will be listed and those collected during the post-treatment period are to be flagged.

The incidence of AEs (new or worsening from baseline) will be summarized by system organ class and preferred term, severity (based on CTCAE grades), type of AE and relation to study treatment.

Deaths reportable as SAEs and non-fatal serious AEs will be listed by patient.

Specific safety event categories will be considered. Such categories consist of one or more well-defined safety events which are similar in nature and for which there is a specific clinical interest in connection with the study treatment(s).

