1.1.4 Treatments (study treatment, concomitant therapies, compliance)

Exposure to everolimus will be summarized for FAS and will be based only on dose administered within this protocol. Study treatment administered during the parent study will not be taken into account.

The following algorithm will be used to calculate the duration of exposure in days:

- Duration of exposure to everolimus (days) = (date of last administration of everolimus) – (date of first administration of everolimus) + 1.

The date of first administration of everolimus is derived as the first date when a nonzero dose of everolimus was administered and recorded on the database of this protocol. The date of last administration of everolimus is defined as is the last date when a nonzero dose of study drug was administered and recorded on the database of this protocol.

The duration of exposure in years is calculated by dividing the duration of exposure in days by 365.25.

The duration includes the periods of temporary interruption.

Everolimus dose administration will be listed by patient.

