1.2 Safety evaluation

For all safety analyses, the safety set will be used.

The overall observation period will be divided into two mutually exclusive segments:

1. on-treatment period: from day of first dose of study medication to 30 days after last dose of study medication
2. post-treatment period: starting at day 30 after last dose of study medication.

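### Optional improvement: the AE tables for a long-term safety study give only number and percentage; add a first-event rate per patient-year and a by-year table

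*SAP*

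**What the plan says.** Protocol Table 3-1 lists one objective, long-term safety, with one endpoint: "Frequency and nature of AEs". There are no secondary objectives and no efficacy assessments, so the AE tables are the main result of the study.

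On those tables, SAP 1.2.1 states: "The incidence of all treatment-emergent AEs (number and percentage) will be summarized by system organ class (SOC), preferred term", followed by maximum severity and relation to treatment. Protocol 10.4.2 is less specific: "The incidence of AEs (new or worsening from baseline) will be summarized by system organ class and preferred term". I read the percentage as a percentage of patients. Deaths and serious AEs are listed by patient.

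The window for treatment-emergent events runs "from day of first dose of study medication to 30 days after last dose of study medication" (SAP 1.2). Treatment has no fixed length, and Protocol 6.1.5 adds: "The study is expected to remain open for 5 years or until such time that enrolled patients no longer need treatment with everolimus".

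SAP 1.1.4 does derive time on drug: "The duration of exposure in years is calculated by dividing the duration of exposure in days by 365.25". It is summarised on its own, for the Full Analysis Set, and ends at the last nonzero dose. Dosing in the parent study is left out. Neither document divides AE counts by time, plans a time-to-first-event summary, or tabulates AEs by interval.

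**The concern.** When follow-up differs between patients, the percentage with an event depends on two things: how fast events occur and how long patients were watched. A low figure may mean a low rate or short follow-up. The percentage also cannot show whether events cluster soon after roll-over, stay level or become more frequent later, and a report on long-term safety is expected to address that. The ingredients exist: Protocol 8.1.1 has the investigator record for each AE "Its duration (Start and end dates or Ongoing at End of Study", and dose dates are in the database. As planned, timing could be recovered only by working through by-patient listings.

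**Working it through.** The plan states no AE rate, sample size or power, so there is no figure to reproduce. What follows illustrates how far the percentage can move. All rates, discontinuation patterns and entry patterns are assumptions.

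**Fixed follow-up.** With a constant first-event rate h and follow-up T, the percentage is 1 − exp(−hT). At h = 0.10 per year it is 4.9% at 0.5 years, 9.5% at 1, 18.1% at 2 and 39.3% at 5.

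**Variable follow-up.** Let time on drug be exponential with parameter m years, capped at c = 5 years (the expected study duration). Put d = 1/m, and let the 30-day tail be 30/365.25 = 0.0821 years (SAP 1.2). Then:

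- mean exposure = m(1 − exp(−c/m))
- percentage = 1 − exp(−0.0821h) × [1 − h/(h+d) × (1 − exp(−(h+d)c))]

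For h = 0.10 and m = 2, mean exposure = 2 × (1 − exp(−2.5)) = 1.84 years, and the percentage = 1 − 0.9918 × [1 − 0.1667 × 0.9502] = 16.5%.

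| m (years) | Mean exposure (years) | Percentage, h = 0.10 | Percentage, h = 0.50 |
|---|---|---|---|
| 1 | 0.99 | 9.8% | 36.0% |
| 2 | 1.84 | 16.5% | 51.7% |
| 4 | 2.85 | 24.2% | 66.5% |

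If entry were instead uniform over 3 years (cap uniform from 2 to 5 years), h = 0.10 gives 9.5%, 15.0% and 20.4% at mean exposure 0.96, 1.62 and 2.29 years.

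**Timing.** Keep m = 2 and c = 5, and let the hazard be h₁ in year 1 and h₂ after it. The percentage is the average over patients of 1 − exp(−[h₁ × time in year 1 + h₂ × time after year 1]). Three patterns give the same 16.5%:

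- 10 per 100 patient-years throughout
- 16.9 in year 1, then 4.2
- 3.9 in year 1, then 15.5

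The planned table cannot tell them apart.

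**Could a reader divide by the planned exposure summary?** Percentage divided by mean exposure, for the three rows above, gives 9.9, 9.0 and 8.5 per 100 patient-years where the assumed rate is 10. It gives 36.2, 28.2 and 23.3 where the assumed rate is 50. The shortcut is close for uncommon events and poor for common ones, because time after the first event stays in the denominator. Pulling the other way, exposure stops at last dose while events count for 30 days more. That tail equals 8.2% of a 1-year exposure (0.0821/1) and 1.6% of a 5-year one (0.0821/5).

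**A trap in building the by-year table.** Suppose each patient is counted once per year but time at risk is cut at the first event ever. Patients with earlier events then stay in the numerator and leave the denominator. With a constant recurrent hazard h, a fraction exp(−h(k−1)) of patients remain event-free at the start of year k, so the apparent rate in year k is h × exp(h(k−1)):

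- h = 0.10: 10.0, 11.1, 12.2, 13.5, 14.9 per 100 patient-years
- h = 0.50: 50, 82, 136, 224, 369 per 100 patient-years

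This is a false rise under constant risk. Restarting the risk set each year returns about 10 or 50 in every year, and a simulation agrees on both counts.

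**Precision.** The number of patients is not stated. For an assumed 3 events in 30 patient-years the rate is 10 per 100. The exact Poisson 95% limits are χ²(0.025; 6)/2 = 0.619 and χ²(0.975; 8)/2 = 8.767 events, or 2.1 to 29.2 per 100 patient-years.

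**The case against.** The strongest reply is that this is a preference. The study is single-arm and descriptive, with no hypothesis and no comparison that unequal follow-up could bias. Number and percentage by SOC, preferred term, severity and relation do deliver the stated endpoint. Exposure is summarised, AEs and dosing are listed by patient, and for uncommon events a reader can get near the rate from those outputs. All of this stands, and it is why the point is an optional improvement. It does not fill the gap for common events or for timing.

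Two limits on the benefit also stand. First, time zero is roll-over. Patients arrive already on everolimus and are expected to have tolerated it (Protocol 6.3.3), and parent-study dosing is excluded (SAP 1.1.4). A reader might infer that a by-year table would show whether events come early or late in everolimus treatment. It would not; it shows years since entering this study. Second, later years describe patients who stayed on drug.

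A last-contact date may not be in the database. Protocol 7.1.6 puts contact attempts in source documents and only the lost-to-follow-up status on the Disposition CRF. The body of Table 7-1 is missing from the text I had, so a fallback date is needed.

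**Conclusion.** The point holds as a low-cost improvement. A reader might infer that the percentage is biased, or that the plan fails its endpoint. The documents do not support that: the percentage is a correct count for a descriptive study, no stated figure is wrong, and the protocol and SAP do not conflict here.

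What is missing is any summary of AE frequency per unit of time or by time since roll-over, in a study whose sole objective is long-term safety. On the assumed inputs, one constant rate of 10 per 100 patient-years gives percentages from 9.8% to 24.2% depending only on follow-up (9.5% to 20.4% with staggered entry), and one percentage fits steady, falling and rising risk. The size in this trial is unknown, because the documents give no rates, discontinuation pattern or patient numbers.

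**What to change.** Keep number and percentage. Add to SAP 1.2.1, on the Safety Set:

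- **(a) First-event rate.** For any treatment-emergent AE, any SAE, each SOC and each preferred term, give patients with a first treatment-emergent event (started or worsened) per 100 patient-years at risk, with an exact Poisson 95% confidence interval. Time at risk starts at the first everolimus dose in this protocol. It ends at the earliest of that first event, last dose plus 30 days, death, withdrawal of consent, last contact (or the last date recorded in the database if no contact date is captured), or data cut-off for ongoing patients. Withdrawal must end time at risk because Protocol 7.1.4.1 then says: "Everolimus must be discontinued and no further assessments conducted".
- **(b) By-year table.** For any treatment-emergent AE, any SAE, SOCs and frequent preferred terms (threshold set in advance), by year since first dose in this protocol, give patients under observation at the start of the year, patients with an event that started or worsened in that year (each counted once per year), and patient-years at risk in that year. Every patient still under observation re-enters the risk set at the start of each year, whatever happened earlier. Risk time within a year ends at that year's first event or at the end of observation. The 30-day tail belongs to the year in which it falls.

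State the limits beside the tables: a roughly constant hazard is assumed within each interval, later years describe those who stayed on drug, years count from roll-over, and intervals are wide when events are few.

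The cost is SAP wording and some programming, mostly from dates already collected, plus a check on the last-contact date. SAEs, now only listed, gain a summary line. No visit or sample size changes.

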1.3 Determination of sample size

No formal sample size calculation is required for this trial since only patients who are still on treatment in the parent study will be enrolled in this trial.

2 Clinical Study Report - Appendix 16.1.9 Documentation of statistical methods

No appendix 16.1.9 will be provided.
